## **7.2. Subject Screening**

Subjects will be screened and if eligible for the study will be randomized on the same day (Day 0 Visit of the controlled treatment phase). Any subject not meeting study enrollment requirements will be considered a screen failure and will not be randomized into the study. Reason for screen failure will be documented. Subjects may rescreen at a future date if their eligibility changes.

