### 7.4 Data Handling Rules

There will be missing data imputation for the primary efficacy analysis. See primary efficacy analysis [Section 9.1](#) for details.

Besides the imputations for the primary endpoint, there will be no imputation of missing data other than for partial or missing dates where complete dates are required to flag data as treatment-emergent or concomitant with treatment. Partial/missing start and end dates for AEs and concomitant medications will be imputed as follows.

Partial/missing start date:

- Dates with missing day only will be imputed as the 1st of the month unless the month and year are same as the month and year of first dose of study medication, in which case missing day will be imputed as the first dose day of study medication.
- Dates with both day and month missing will be imputed as 1 Jan unless the year is same as the year of first dose of study medication, in which case missing day and month will be imputed as the first dose day and month of study medication.

- 
- Completely missing dates will be imputed as the first dose date of study medication unless the end date is on or before the first dose date of study medication, in which case missing date will be imputed as 1 Jan of the same year as the end date.

Partial/missing end date:

- Dates with missing day only will be imputed as the last day of the month.
- Dates with both day and month missing will be imputed as 31 Dec.
- If the ongoing flag is missing or “Yes” then the date will not be imputed unless death date is available, in which case the missing date will be imputed as the death date. If ongoing is “No” then the missing end date will be imputed as the last dose date.
- If the imputed date is after the date of death, then the end date will be set equal to the date of death.
- The original dates will be displayed in data listings and the imputed dates will be used in derivations only (study day, treatment-emergence status, etc.).

Partial/missing start dates for initial and current NK stage will be imputed as follows.

- Dates with missing day only will be imputed as the 16th of the month.
- Dates with both day and month missing will be imputed as 1 July.
- Completely missing dates will not be imputed. The current NK stage duration will be left as missing.

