## **10.0 SAFETY EVALUATION**

### **10.1 Adverse Events**

---

AEs verbatim descriptions will be coded using a current version of MedDRA. A treatment-emergent adverse event (TEAE) will be defined as any AE that occurs on or after the start time of the first study drug administration.

An overall summary of TEAEs will be presented as the number and percentage of subjects with at least one event on the following categories:

- TEAEs
- Severe TEAEs
- Treatment-related TEAEs
- Severe and treatment-related TEAEs
- Serious TEAEs
- Serious treatment-related TEAE
- TEAEs leading to treatment discontinuation
- Treatment-related TEAEs leading to treatment discontinuation
- TEAEs leading to Death (with an outcome of Fatal)

TEAEs will be summarized by System Organ Class (SOC) and Preferred Terms (PT) by treatment group. A patient will be counted only once by the highest severity grade within a system organ class and preferred term, even if the patient experienced more than 1 TEAE within a specific system organ class and preferred term. Following incidence tables of TEAEs will be presented:

- TEAEs
- TEAEs by severity
- Treatment-related TEAEs
- Treatment-related TEAEs by severity
- Serious TEAEs

Systemic TEAEs and ocular TEAEs will be summarized separately. Ocular TEAEs will be summarized by study eye and non-study eye.

All AEs will be listed by subjects.

SAEs for death will be listed if applicable and a narrative included.

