 Subjects whose cornea is healed at Week 8 will be assessed for sustained healing at Week 10. Subjects whose cornea is not healed at Week 8 will be unmasked; subjects in the CSB-001 arm will exit the study, subjects in the vehicle arm are eligible to enter the uncontrolled treatment phase and receive an 8-week course of treatment with CSB-001.  
 Subjects whose cornea is completely healed at Week 8 and sustained until Week 10 will exit the study. Subjects whose cornea is not healed at Week 10 will be unmasked; subjects in the CSB-001 arm will exit the study, subjects in the vehicle arm are eligible to enter the uncontrolled treatment phase and receive an 8-week course of treatment with CSB-001.  
 Ensure exit procedures are conducted at the time of study exit for subjects exiting prior to the Week 8 Visit. Only assessments not conducted as part of a planned or unscheduled study visit at the time of study exit should be performed.  
 Record adverse events after test article instillation on Day 0  
 Ocular tolerability assessment to be conducted immediately after in-office study drug instillation at specified visits  
 VA and slit-lamp will be assessed in both the study and non-study eyes in the initial safety phase (i.e., first 12 subjects randomized).  
 At Day 0, corneal sensitivity assessed using a cotton wisp will be performed to determine study eligibility. Corneal sensitivity will also be assessed using a Cochet-Bonnet aesthesiometer if available at the site. At Week 8, sensitivity will only be assessed in subjects at clinical sites with access to a Cochet-Bonnet aesthesiometer.  
 Administer first dose in the clinic

Protocol CSB-C20-003

Statistical Analysis Plan

Claris Biotherapeutics, Inc.

Version 1.0 DRAFT

Open-Label Uncontrolled Treatment Phase												
(Subjects randomized to vehicle in the controlled treatment phase whose cornea is not healed at Week 8 or whose cornea is healed at Week 8 but not sustained for two weeks until Week 10 are eligible to receive an 8-week course of treatment with CSB-001)												
Study Procedures	Day 0 1* Entering at Wk 8 Controlled Visit	Day 0 1* Entering at Wk 10 Controlled Visit	Wk 1	Wk 2	Wk 3	Wk 4	Wk 5	Wk 6	Wk 7	Wk 8 	Wk 10 	Early Exit 
Previous/Change in Medical History and Concomitant Meds (Systemic and Ocular)			X	X	X	X		X		X	X	X

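### SAP 7.4 dates an adverse event that has no onset date and ended on Day 0 back to 1 January, which makes it non-treatment-emergent

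*SAP*

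**What the plan says.** SAP 7.4 sets out how missing dates are filled, with the same rules for AEs and concomitant medications. For a start date with no day, month or year:

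- Default: "Completely missing dates will be imputed as the first dose date of study medication".
- Exception: the default holds "unless the end date is on or before the first dose date of study medication"; if it is, the start becomes 1 January of the year in which the event ended.

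Listings keep the recorded dates, and "the imputed dates will be used in derivations only (study day, treatment-emergence status, etc"). A start date known only to the year, where that is the year of first dose, is set to the first-dose date. So is one missing only the day, in the month and year of first dose.

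SAP 10.1 defines a TEAE as "any AE that occurs on or after the start time of the first study drug administration". Its overall summary and all its incidence tables count TEAEs only; a listing covers all AEs.

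On timing, Protocol 7.2 says "Subjects will be screened and if eligible for the study will be randomized on the same day", and SAP 3.0 places consent at that Day 0 visit. Protocol 12.1 records AEs from consent to the end of the study, with the date and time of both onset and resolution. In SAP Appendix 1, footnote 9 has the first dose given in the clinic, and footnote 5 says "Record adverse events after test article instillation on Day 0".

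For end dates, if an AE is marked as not ongoing and its end date is missing, "then the missing end date will be imputed as the last dose date". The only limit on the imputed end is the date of death.

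**The concern.** The exception suits medications. Protocol 7.4 collects these back three months before Day 0, so a start well before the first dose is plausible. It does not suit AEs, because no AE in this trial can have started before consent, and consent and first dose fall on the same day.

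The exception also includes an end date equal to the first-dose date. A reaction to the first drop that clears the same day meets that condition if its onset date was left blank. The rule then gives it an onset before treatment, and the TEAE tables lose it. Undercounting is the non-conservative direction for safety, and same-day reactions are what the Day 0 query is meant to capture.

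**Working it through.** The documents state no figure on this point, so the check is to apply the rule as written.

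**Inputs.** F = first-dose date (Day 0). E = recorded AE end date. S = AE start date, completely missing. Consent is on Day 0.

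**Rule (SAP 7.4).** Imputed start S* = 1 January of the year of E if E ≤ F; otherwise S* = F.

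**Flag (SAP 10.1).** TEAE if S* is on or after F. An imputed date has no clock time, so I assume that S* = F counts as treatment-emergent, the evident purpose of the default.

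**Results.** The calendar dates are chosen for illustration.

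| First dose F | AE end E | Imputed start S* | S* − F (days) | TEAE? |
|---|---|---|---|---|
| 15 Jun 2022 | 15 Jun (Day 0) | 1 Jan 2022 | −165 | No |
| 15 Jun 2022 | 16 Jun (Day +1) | 15 Jun 2022 | 0 | Yes |
| 31 Dec 2022 | 31 Dec (Day 0) | 1 Jan 2022 | −364 | No |
| 2 Jan 2022 | 2 Jan (Day 0) | 1 Jan 2022 | −1 | No |
| 1 Jan 2022 | 1 Jan (Day 0) | 1 Jan 2022 | 0 | Yes |

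The Day 0 event is kept only when the first dose itself falls on 1 January.

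**Comparison with the SAP's own partial-date rule.** Take the AE in the first row and suppose the onset year, 2022, was recorded. The start is then set to 15 June 2022 and the AE is a TEAE, with the same Day 0 end date. Knowing less about the onset therefore moves the event out of the tables.

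**With the exception limited to E < F.** In all four Day 0 rows S* = F, and the AE is a TEAE. The Day +1 row does not change. An end date before Day 0 still gives a non-TEAE, but with consent on Day 0 such an AE should not exist. For AEs, then, the exception in practice reaches only Day 0 end dates.

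**End-date rule (housekeeping).** Imputed end minus onset, where the AE is not ongoing and its end date is missing:

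- Last dose Day 56, onset Day 60: 56 − 60 = −4 days.
- Last dose Day 56, onset Day 77 (Week 10 plus 7 days): 56 − 77 = −21 days.
- Last dose Day 54 (Week 8 minus 2 days), onset Day 77: 54 − 77 = −23 days.
- Dosing stopped on Day 14, onset Day 42: 14 − 42 = −28 days.

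Taking the later of onset and last dose makes each of these 0.

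**The case against.** The strongest reply is that the trigger is nearly empty. Day, month and year of onset must all be missing while the end is known to be Day 0. Protocol 12.1 asks for onset date and time, the first dose is given in the clinic, and Protocol 14.1 and 14.3 provide source verification and queries. In-clinic reactions are among the least likely to lack an onset date. This stands, and it limits the point to a few events at most.

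A reader might infer that every affected event is misclassified. The documents do not support that. AEs are recorded from consent, and footnote 1 of SAP Appendix 1 places the other Day 0 procedures before the first dose; these include fluorescein imaging, Schirmer's test, IOP and dilated ophthalmoscopy. A reaction to one of these that began before the drop is correctly non-TEAE. For such an event the imputed date is wrong, but the status is right by chance.

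A reader might also infer that first-dose reactions in general drop out of the safety results. They do not. Only fully undated ones are affected, and these stay in the AE listing with their recorded dates. Instillation tolerability is also captured by a questionnaire straight after the in-office dose (Protocol 7.6) and summarized by visit (SAP 10.6). The rule is the same in both arms, although that does not protect the comparison if same-day reactions are more frequent in one of them.

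Finally, the end-date rule might be read as distorting the AE results. It does not. TEAE status depends on onset, no AE duration analysis is planned, and listings show recorded dates. SAP 7.4 also limits imputation to dates needed for the treatment-emergent or concomitant flags.

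**Conclusion.** The point holds for the start-date rule and is minor. For an AE with a completely missing start that ended on Day 0, SAP 7.4 imputes a start up to about a year before consent and removes the event from the TEAE summaries. For a reaction that began after the drop, this is wrong and non-conservative; for one that began before it, the flag is correct by accident. The number of events cannot be computed from the documents but should be small.

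This assumes consent on Day 0, as SAP 3.0 has it; a rescreened subject (Protocol 7.2) might have consented earlier. It also takes the first dose to be that of the controlled phase, because SAP 7.4 does not say which phase's doses apply to subjects who enter the open-label phase. The end-date rule can give an end before the start, but no planned table changes.

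**What to change.** Separate the AE start-date rule from the medication rule in SAP 7.4. For AEs:

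- Set a completely missing start to the first-dose date unless the end date is strictly before that date.
- Count an undated AE that ended on Day 0 as treatment-emergent unless recorded times show it was pre-dose, for example a resolution time earlier than the first dose.
- Never impute an AE start before the consent date.

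As housekeeping only, where an AE is not ongoing and its end date is missing, let the imputed end be no earlier than the AE start.

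The cost is a few sentences and a small programming change, to be made before the controlled-phase data are locked and unblinded (SAP 7.1). The downside is that a few undated pre-dose Day 0 events may be counted as TEAEs, which is the cautious direction.

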## 7.5 Study Day and Time-to-Event

For the purpose of this document and time-to-event duration calculation,

- D0 is the screening/randomization (baseline visit) day
- Time to corneal healing (0 mm lesion size) based on assessments by the CRC is defined as: the earliest Digital Imaging of Corneal Fluorescein Staining date with corneal healing, as assessed by the CRC, from the Date of randomization (D0)
- Time to corneal healing (0 mm lesion size) based on assessments by the investigator is defined as: The earliest date of investigator assessment with corneal healing from the Date of randomization (D0)
- Time to  $\geq 20\%$  decrease in lesion size (maximum diameter) assessed by the CRC is defined as: The earliest date of Digital Imaging of Corneal Fluorescein Staining taken with  $\geq 20\%$  decrease in lesion size assessed by the CRC from the Date of randomization (D0)

## 7.6 Interim Analyses

There is no interim analysis planned for this study.

## **8.0 STATISTICAL SUMMARIES**

### **8.1 Subject Disposition**

The number and percentages of subjects screened, randomized, FAS, ITT, safety analysis set, PP Set, completed the study and discontinued from the study will be reported, along with the reason for discontinuation.

Only counts will be reported for screened subjects.

### **8.2 Demographic and Baseline Characteristics**

Demographic/baseline characteristics including age (years), sex, race, ethnicity, NK stage, and duration of current NK stage will be summarized and presented by treatment group.

Descriptive statistics will be presented for the continuous variables. Frequency counts and percentages will be presented for the categorical variables for each category.

### **8.3 Medical History**

Medical history terms will be coded using the Medical Dictionary for Regulatory Activities (MedDRA) dictionary. Medical history will be summarized by system organ class (SOC) term and preferred term for each cohort by treatment group. For subjects with the same SOC and preferred term occurring more than once, the first occurrence will be tabulated. Systemic medical history and ocular medical history will be summarized separately. Ocular medical history will be summarized by study eye and non-study eye.

Conditions will be listed, including the verbatim investigator description of the relevant medical condition, the coded terms (SOC, preferred term), start date, end date, and whether or not the condition is ongoing.

### **8.4 Prior and Concomitant Medications**

Prior and concomitant medications will be coded with the World Health Organization Drug Dictionary (WHO-DD), and summarized by drug class (Anatomical Therapeutic Chemical [ATC] Level 3) and preferred term; a subject will be counted only once for each medication.

Concomitant medications are medications which started 1) prior to initiation of study treatment administration and continuing for any period of time following the Day 0 administration of study treatment or 2) at any time following the Day 0 administration of study treatment. Prior medications are medications which are started before the Day 0 administration of study drug.

All medication will be listed with the prior medications flagged. Systemic prior and concomitant medication, and ocular prior and concomitant medication will be summarized separately. Ocular prior and concomitant will be summarized by study eye and non-study eye.

---

## 8.5 Protocol Deviations

Protocol deviations recorded will be reviewed and major deviations will be identified prior to database lock and unblinding of the study.

Protocol deviations will be summarized by pre-specified category from the CRF, by major or minor, and a subject listing will be presented.

## 8.6 Study Drug Administration

For study drug administration, descriptive statistics of the following parameters will be presented in Safety Analysis Set.

- Total number of weeks on study
- Total number of doses planned
- Total number of doses administered
- Total number of doses missed

Subject listing of study drug administration will be presented

## 9.0 EFFICACY EVALUATION

### 9.1 Primary Efficacy Endpoint

#### 9.1.1 Primary Analyses

Analyses of the primary efficacy endpoint will follow the estimand framework stated in [Section 2.2.1](#). Full analysis set will be used for the efficacy analyses.

The primary efficacy endpoint is the proportion of subjects achieving complete corneal healing defined as absence of corneal staining in the area of the defect/ulcer (i.e., 0 mm lesion) at Week 8 and the absence of corneal staining in the area of the defect/ulcer (i.e., 0 mm lesion) two weeks later at Week 10 as assessed by a central reading center.

Chi-squared test will be used to compare each CSB-001 active treatment group (QID) to vehicle. The proportion and associated 95% confidence interval will be reported by each treatment arm. Difference in the proportions between treatment arms and associated 95% confidence interval will also be reported.

Missing data of the primary efficacy endpoint will be imputed as follow:

- Subjects with missing Week 8 data for any reason will be imputed as non-responders
- Subjects who demonstrate corneal healing at Week 8 and are missing Week 10 data will be imputed as non-responders

---

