**2.2.3 Exploratory Efficacy Endpoints**

- Proportion of subjects achieving corneal healing at each of Weeks 2, 6, and 8 assessed by the CRC
- Proportion of subjects with corneal healing defined as less than 0.5 mm fluorescein staining (the lower limit of reliable slit-lamp assessment) in the lesion area, assessed by the CRC at each of Weeks 4 and 8
- Time to  $\geq 20\%$  decrease in lesion area from baseline assessed by the CRC
- Change in lesion size (PED or ulcer maximum diameter) from baseline at each of Weeks 2, 4, 6, 8 and 10 assessed by the CRC
- Change in lesion area (PED or ulcer) from baseline at each of Weeks 2, 4, 6, 8 and 10 assessed by the CRC
- Change in pinhole distance VA in the study eye from baseline to each of Weeks 4 and 8 (and Week 10 in the subset of subjects completing Week 10)
- Proportion of subjects achieving a  $\geq 10$ -letter gain in the study eye from baseline in pinhole distance VA at each of Weeks 4 and 8
- Change in corneal sensitivity inside the lesion from baseline (measured by Cochet-Bonnet aesthesiometer) at Week 8 (data from the subset of subjects with this data)
- Change in Schirmer's test scoring at Week 8

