#### **4.0 RANDOMIZATION AND BLINDING**

This is a multi-center, randomized, double-masked, vehicle-controlled, parallel-group safety and efficacy study. Approximately 128 subjects (64 per treatment arm) will be randomized in the study to complete approximately 96 subjects (48 per treatment arm).

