#### **5.0 SAMPLE SIZE CONSIDERATIONS**

With the assumption that the proportion of subjects that will achieve complete corneal healing for the CSB-001 and vehicle are 60% and 30%, respectively, 48 subjects per arm (a total of 96 subjects) will have 80% power to detect the difference of 30% at a two-sided alpha 0.05 based on a Chi-squared test. With a predicted dropout rate of ~10% and the risk of inadequate numbers of corneal defect images for interpretation by the central reading center at key visits (Day 0, Week 8, and Week 10), approximately 128 subjects will be randomized at 1:1 ratio (CSB-001: vehicle).

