### 9.1.2 Sensitivity Analyses

Sensitivity analyses based on different missing data imputation rules will be conducted for the primary endpoint. Specific imputation rules are:

1. Completers Analysis (Week 8 Observed) Data Imputation
  - Subjects who do not complete the Week 8 Visit will be imputed as missing
  - Subjects who demonstrate corneal healing at Week 8 and are missing Week 10 data will be imputed as missing at Week 8
2. LOCF Data Imputation
  - Subjects with missing Week 8 and/or Week 10 data will have their last observed data carried forward
3. Tipping point analyses will be performed.
  - In CSB-001 arm, one responder will be changed to be a non-responder, and the same primary analysis will be performed. In CSB-001 arm, two responders will be changed to be non-responders, and the same primary analysis will be performed again. This will continue until X responders in CSB-001 arm are changed to be non-responders when p-value becomes not statistically significant. In these analyses, no changes will be made to the vehicle arm.
  - In the vehicle arm, one non-responder will be changed to be a responder, and the same primary analysis will be performed. In the vehicle arm, two non-responders will be changed to be responders, and the same primary analysis will be performed again. This will continue until X non-responders in the vehicle arm are changed to be responders when p-value becomes not statistically significant. In these analyses, no changes will be made to the CSB-001 arm.

In addition, instead of Chi-squared test, Cochran–Mantel–Haenszel (CMH) test stratified by stage 2 NK vs stage 3 NK will be used to analyze the primary endpoint as another sensitivity analysis.

Per-protocol analysis set will also be used to analyze the primary endpoint as exploratory analyses.

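### The primary chi-squared test is valid but leaves out baseline lesion diameter, and uses NK stage only in a sensitivity analysis; pre-specified adjustment for both is a cheap gain in efficiency

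*SAP*

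**What the plan says.** The primary analysis has no covariates: "Chi-squared test will be used to compare each CSB-001 active treatment group (QID) to vehicle" (SAP 9.1.1; protocol 13.3.1 agrees). The estimand in SAP 2.2.1 is summarised by the difference in responder proportions, and missing Week 8 or Week 10 outcomes count as non-response.

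Stage enters once, through a CMH "test stratified by stage 2 NK vs stage 3 NK will be used to analyze the primary endpoint as another sensitivity analysis" (SAP 9.1.2; also protocol 13.3.1).

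The SAP abbreviation list defines lesion size as the maximum diameter in mm measured by the CRC. A baseline value is needed for the exploratory endpoint "Change in lesion size (PED or ulcer maximum diameter) from baseline" (SAP 2.2.3), but no analysis of the primary endpoint uses it.

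On power, SAP 5.0 says that 48 per arm "will have 80% power to detect the difference of 30% at a two-sided alpha 0.05 based on a Chi-squared test", with assumed response of 60% against 30%. About 128 subjects are to be randomized, 64 per arm, to allow for losses: "With a predicted dropout rate of ~10% and the risk of inadequate numbers of corneal defect images for interpretation". Day 0 is among the visits named as at risk.

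**The concern.** The endpoint is closure to 0 mm at Week 8, sustained to Week 10, so the diameter at Day 0 is a natural candidate predictor. The plan already treats stage as relevant by stratifying a sensitivity test on it. If the two variables do predict healing, an unadjusted test leaves explainable outcome variance in the error term and gives up power.

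Chance imbalance is the second issue. In a trial of this size, a difference between arms in baseline lesion size moves the unadjusted estimate directly. Adjustment planned in advance largely removes that shift; adjustment chosen after the imbalance has been seen would carry little weight.

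**Working it through.** **Inputs.** From the documents: 60% and 30% response, 48 evaluable and 64 randomized per arm, two-sided alpha 0.05, missing outcome = non-response. Assumed, because the documents are silent: 35% stage 3, standardised normal diameter, and three strengths of prognosis given as odds ratios for stage 3 and per SD of diameter: weak (0.5, 0.67), moderate (0.4, 0.5), strong (0.33, 0.4). These correspond to within-arm explained variance R² of about 0.05, 0.12 and 0.18.

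**1. The plan's own figure.** Without continuity correction, n per arm = [1.96·√(2·0.45·0.55) + 0.842·√(0.24 + 0.21)]² / 0.30² = 42. With the correction it is 49. Exact enumeration at 48 per arm gives 80.0% power for the corrected test, so the stated 80% reproduces on that reading. For the uncorrected test:

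- SE under the null = √(2·0.45·0.55/48) = 0.1016
- SE under the alternative = √((0.24 + 0.21)/48) = 0.0968
- Power = Φ[(0.30 − 1.96·0.1016)/0.0968] = Φ(1.04) = 85.1%

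The gains below start from the uncorrected test.

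**2. Effect of adjustment, 48 per arm.** Multiply both standard errors by √(1 − R²). For R² = 0.10 the factor is 0.949, and power = Φ[(0.30 − 1.96·0.0963)/0.0919] = Φ(1.21) = 88.7%.

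| R² | Power | Gain (points) |
|---|---|---|
| 0 | 85.1% | 0 |
| 0.05 | 86.9% | 1.8 |
| 0.10 | 88.7% | 3.5 |
| 0.15 | 90.4% | 5.3 |
| 0.20 | 92.1% | 6.9 |

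Simulation of the three named settings gave gains of 1.1, 3.8 and 5.5 points.

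**3. Effect under the non-responder rule, 64 per arm.** If 25% of outcomes are set to failure (1 − 48/64), the rates become 45% and 22.5%, and unadjusted power is 77.4%. If the imputed failures are random with respect to the covariates, R² shrinks. The explained variance is multiplied by 0.75² = 0.5625 while the total variance barely changes:

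- CSB-001: 0.5625·0.24/0.2475 = 0.55
- Vehicle: 0.5625·0.21/0.1744 = 0.68

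With an average factor of about 0.61, R² of 0.05, 0.12 and 0.18 becomes about 0.03, 0.07 and 0.11. Interpolating the analytic gains at this base (0.8, 2.1, 4.2 and 6.4 points at R² of 0.02, 0.05, 0.10 and 0.15) gives roughly 1.3, 3.0 and 4.7 points. Simulation with a random 25% set to failure gave about 1 to 4 points.

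**4. No prognostic value.** With both effects at zero, simulated differences between adjusted and unadjusted power were within Monte Carlo error of zero.

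**5. Which covariate matters.** The stage-stratified CMH alone added at most about 1.5 points in simulation (85.4% to 86.9% in the strongest setting run). Most of any gain must come from diameter.

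**6. Chance imbalance.** A two-standard-error imbalance in mean diameter at 48 per arm is 2·√(2/48) = 0.41 SD. In simulation it moved the unadjusted difference by about 3.5, 5.4 or 6.9 points (weak, moderate, strong), against a planned effect of 30.

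**7. Type I error.** Simulated rates were about 5.1% to 6.0% for adjusted tests and 5.0% to 5.7% for chi-squared.

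**The case against.** The plan is defensible as it stands. Randomization makes the chi-squared test valid, and chance imbalance does not bias it on average. The test matches the sample-size basis and the estimand, and on the plan's own assumptions it reaches 80% power. Stage already has a pre-specified analysis. All of this stands, and it is why the point is an improvement and not a correction. It does not remove the gain available from diameter, which no analysis of the primary endpoint uses.

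A reader might infer a firm gain of up to about 7 points. The documents do not support that. In the non-responder setting, a rise from 78% to 85% appears only when imputed failures are made to depend on stage and diameter as strongly as true non-healing does. Step 3 shows what remains when they do not.

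A reader might also infer that the change is free. It is not:

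- The tipping-point rule in SAP 9.1.2 changes one outcome at a time and repeats the primary analysis. With covariates, it matters whose outcome is changed: in 155 significant simulated trials, two flip orders gave different tipping counts in 72%.
- The ITT set (SAP 6.2) keeps subjects without stage 2 or 3 per the CRC, who would have no CRC stage for the model.
- Day 0 diameter may be missing. SAP 7.4 allows no imputation beyond the primary endpoint and dates, so a complete-case model would drop subjects.
- SAP 9.2 ties the dichotomous key secondary endpoints to the primary method.
- A p-value from one procedure and an interval from another could disagree.

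Each of these can be settled with a sentence in the SAP.

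**Conclusion.** The point holds as a low-cost efficiency improvement. The primary test is valid, but it ignores CRC baseline diameter and leaves stage to a sensitivity analysis. With 35% stage 3 and the stated range of odds ratios, adjustment adds about 1 to 5.5 points of power at 48 evaluable per arm, and about 1 to 4 points at 64 per arm with a random 25% imputed as non-responders. It adds nothing if the covariates are not prognostic. Stage mix and prognostic strength are assumptions, so the size is conditional. The simulated type I error is slightly higher than for chi-squared, so part of a 1-point gain could reflect test size; a small-sample variance check is needed.

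**What to change.** Before unblinding, amend SAP 9.1.1 and protocol 13.3.1 as follows.

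- **Primary analysis:** a logistic model with treatment, baseline NK stage and CRC baseline maximum diameter (continuous), standardised to the difference in proportions. Take the p-value and 95% CI from the same procedure, and check a small-sample variance correction.
- **Sensitivity:** keep the unadjusted chi-squared test and the stage-stratified CMH.
- **Covariates:** state whether stage comes from the CRC or the investigator. Give a simple rule for missing Day 0 diameter, such as single imputation from baseline data pooled over arms, so that no full-analysis-set subject is dropped.
- **Linked analyses:** reword SAP 9.1.2, 9.1.3 and 9.2 so that the tipping-point analyses, the ITT repeat and the dichotomous secondary endpoints stay on the unadjusted chi-squared test.
- **Wording:** refer to the single CSB-001 arm in SAP 9.1.1, since the present sentence implies several active groups.

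The cost is one more model to specify and these wording changes. No new data are needed.
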